## **Appendix 2: American College of Rheumatology (ACR) Measures**

- The following 66/68 joints will be assessed for tenderness and swelling
- Number of tender joints:

The 68 joints to be examined for tenderness are: temporomandibular (2), sternoclavicular (2), acromioclavicular (2), shoulder (2), elbow (2), wrist (2), metacarpophalangeal (10), thumb interphalangeal (2), distal interphalangeal (8), proximal interphalangeal (8), hip (2), knee (2), ankle mortise (2), ankle tarsus (2), metatarsophalangeal (10), interphalangeal of great toe (2) and proximal/distal interphalangeal of the toes (8).

- Number of swollen joints:

The 66 joints to be examined for swelling are the same as those examined for tenderness, except the hip joints are not included.

- Patient's assessment of RA pain

On a 100 mm non-anchored visual analog scale, from no pain to unbearable pain.

- Patient's global assessment of disease activity

On a 100 mm non-anchored visual analog scale, from no arthritis activity to maximal arthritis activity, after the question "Considering all the ways your arthritis affects you, draw a line on the scale for how well you are doing".

- Physician's global assessment of disease activity

On a 100 mm non-anchored visual analog scale, from no arthritis activity to maximal arthritis activity.

- Health Assessment Questionnaire disability index – HAQ-DI©

### Appendix 3: FACIT Fatigue Scale

Below is a list of statements that other people with your illness have said are important. By circling one (1) number per line, please indicate how true each statement has been for you during the past 7 days.

#### FACIT-Fatigue Subscale Scoring Guidelines (Version 4)

Instructions:\*

1. Record answers in "item response" column. If missing, mark with an X
2. Perform reversals as indicated, and sum individual items to obtain a score.
3. Multiply the sum of the item scores by the number of items in the subscale, then divide by the number of items answered. This produces the subscale score.
4. The higher the score, the better the QOL.

Subscale	Item Code	Reverse item?	Item response	Item Score
FATIGUE	HI7	4 -	____	= _____
SUBSCALE	HI12	4 -	____	= _____
	An1	4 -	____	= _____
	An2	4 -	____	= _____
	An3	4 -	____	= _____
	An4	4 -	____	= _____
	An5	0 +	____	= _____
	An7	0 +	____	= _____
	An8	4 -	____	= _____
	An12	4 -	____	= _____
	An14	4 -	____	= _____
	An15	4 -	____	= _____
	An16	4 -	____	= _____
				_____

*Sum individual item scores:*

*Multiply by 13:*

*Divide by number of items answered:*

*Score range: 0-52 = Fatigue Subscale score*

PK	Pharmacokinetics
PPS	Per-Protocol Set
PT	Preferred Term
PtGA	Patient's global assessment of disease activity
RA	Rheumatoid Arthritis
RBC	Red Blood cell Count
SAE	Serious Adverse Event
SAP	Statistical Analysis Plan
SCR	Screening
SDTM	Study Data Tabulation Model
SD	Standard Deviation
SJC66	Swollen Joint count on 66 Joints
SJC28	Swollen Joint Count on 28 Joints
SOC	System Organ Class
SP1	Study Period 1
SP2	Study Period 2
TEAE	Treatment Emergent Adverse Event
TJC68	Tender Joint Count on 68 Joints
TJC28	Tender Joint Count on 28 Joints
TNF	Tumor Necrosis Factor
TP	Treatment Period
VAS	Visual Analog Scale
WBC	White Blood cell Count
WHO	World Health Organization

1 Introduction

This document describes the detailed statistical methodology for the analysis of the Clinical Study GP17-302. It describes the planned analysis for Study Period 1 (SP1) of the study, i.e. up to the Week 24 visit, which includes the primary analysis at the Week 12 visit, and the analysis of Study Period 2 (SP2) data from Week 24 to Week 48, as well as the overall analysis of entire study data. This SAP covers all aspects of the statistical methodology with regard to the analysis of efficacy, safety, immunogenicity and local tolerability at the injection sites.

Any deviation from the final statistical analysis plan (SAP) after CDBL will lead to an SAP addendum and will be described in detail in the CSR, along with reasons for the change.

This version of the SAP will be finalized and approved in the Document Management System before the database is locked and before unblinding of the sponsor team.

Study Design

This study has a parallel-group, randomized, double-blind design and it is planned to randomize approximately 308 patients with moderate to severe active RA at approximately 110 study sites worldwide. A screening period of up to 4 weeks was used to assess patient's eligibility. All patients had to be on a stable dose of MTX at least 4 weeks prior to randomization and continue throughout the study on this dose.

At the baseline visit (Day 1, Visit 2); eligible patients were randomized using a 1:1 ratio to one of the two treatment arms: GP2017 or US-licensed Humira®. Randomized patients entered a 24-week treatment phase Study Period 1 and were treated with s.c. injection of either GP2017 or US-licensed Humira®. Study drug administration was performed at the site by designated unblinded personnel. At Week 24 all patients were evaluated for their DAS28-CRP response (based on CRP taken at Week 22). Patients who did not show at least a moderate DAS28-CRP response had their final assessment at Week 24 and did not continue in the study.

Irrespective of their treatment during Study Period 1, all patients with at least a moderate response at Week 24 by DAS28-CRP score, were to be switched to or continued with subcutaneous injection of GP2017 from Week 24 up to Week 46. End of Study (EoS) Visit was to be performed at Week 48.

2 Statistical and analytical plans

Data will be analyzed by Sandoz according to the data analysis described in Section 9 of the study protocol. Important details are given in the following sections, and the statistical methods will also be summarized as applicable in Appendix 16.1.9 of the CSR.

2.1 Study documents and general considerations

2.1.1 Study documents

The following study documents are considered for the finalization of the SAP.

- Study protocol version 4, dated 01-Feb-2017
- Electronic Case Report Form (eCRF) version 8.0, dated 25-Sep-2017

- BDRM minutes version final 1.0, dated 19-Mar-2018

2.1.2 General considerations

Raw data listings, summary tables, figures and statistical tests will be generated using the SAS® Version 9.4 or higher.

All clinical data, including laboratory, immunogenicity, and pharmacokinetics data will be provided as raw data from an external database. CDISC SDTM 3.1.2 amendment 1 compliant SAS® datasets will be prepared. The final SDTM files will also include variables indicating the actual and planned treatment assigned.

Coding of corresponding data (e.g. by Medical Dictionary for Regulatory Activities [MedDRA] or World Health Organization [WHO]-drug dictionary), and ATC coding is included in the SDTM datasets.

Appropriate SAS® programs will be prepared and validated according to standard operating procedures.

The following descriptive statistics will be shown in summary tables:

- Continuous variables: n (number of patients with evaluable data), mean, standard deviation (SD), minimum, median, maximum. Quartiles will be presented as appropriate.
- Categorical variables: Count and percentage of each category. A row denoted “Missing” will be included in count tabulations where necessary to account for dropouts and missing values. Unless otherwise specified, the denominator for all percentages will be the number of patients in the treatment group within the analysis set of interest. Percentages will not be provided if the number is zero.

The same number of decimal places as in the raw data will be presented when reporting minimum and maximum, 1 more decimal place than in the raw data will be presented when reporting mean, median and quartiles, and 2 more decimal places than in the raw data will be presented when reporting SD and SE.

For the derived variables, appropriate precision should be provided in CSR appendix data listing. E.g., for the DAS28-CRP and DAS28-ESR, 2 decimal places will be kept in the data listing, the decimal places of the descriptive statistics will then follow the rules above accordingly (i.e., treat raw data as 2 decimal places).

In general, for by-visit summaries, data recorded at the nominal visit will be presented. With the exclusion of AEs (see in Section 2.3.2.1), only data up to study discontinuation (i.e., including End of Study visit) will be analyzed, but all the data will be listed. End of Study visit within the nominal visit windows on a condition of absence of a nominal visit will be assigned to the nominal visit (see in Section 4.1.4), otherwise it will be included as a separate visit regardless of the day it took place. Unless otherwise noted, unscheduled visits will not be included in by-visit summaries. However unscheduled measurements will be presented in the listings.

Date imputations will be performed as described in [Appendix 1](#) and [Appendix 2](#). Imputed dates will be used for further derivations, only the not imputed partial dates will be presented in the listings.

Study Period 1 summary tables will be presented by treatment as

- GP2017
- Humira
- Total

Study Period 2 summary tables will be presented by treatment as

- Continued GP2017
- Humira to GP2017
- Total

Overall (including entire study) summary tables will be presented by treatment as

- GP2017
- Humira/Switched GP2017
- Total

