2.4.1 Analysis of the primary endpoint

The following statistical hypotheses will be used to assess equivalence between GP2017 and US-licensed Humira® with regards to DAS28-CRP change from baseline at Week 12:

$H_0: |GP2017 - \text{Humira}^\circledR| \geq 0.6$ versus $H_1: |GP2017 - \text{Humira}^\circledR| < 0.6$

To address both EMA and FDA regulatory requirements for establishing therapeutic equivalence both 95% and 90% confidence intervals will be estimated and used to assess equivalence of DAS28-CRP change from baseline at Week 12.

Therapeutic equivalence in terms of DAS28-CRP will be concluded if the 95% (as required by EMA) or 90% (as required by FDA) confidence interval for the difference in DAS28-CRP change from baseline at Week 12 between the two treatment groups is completely contained within the interval [-0.6, 0.6]. This is statistically equivalent to calculating two independent one-sided tests at 2.5%/5% alpha level (one in each direction), of which both have to be successful.

A mixed-model repeated measures (MMRM) analysis will be performed for DAS28-CRP change from baseline up to Week 12 as the endpoint, including treatment, stratification factors (region, body weight category, prior systemic therapy), time, the interaction between time (visits) and treatment all as categorical variables, and baseline DAS28-CRP as a continuous variable in the model.

DAS28CRP CFB = treat + strata + time + (time*treat) + baseline DAS28CRP

In the case that the IRT and eCRF values of the stratification factors differ the correct definition of the stratification factors used for the primary analyses will be based on the clinical database.

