4.1.4 Visit windows

Study data for a scheduled visit (weeks 2, 4, 12, 24 and 48) should be entered on to the correctly designated eCRF page for that visit. However, in order to be considered per protocol a visit needs to fall within a window of time around the target date for the visit. In the protocol this is defined as a window of ± 2 days for SP1 and ± 3 days for SP2 around the target date, calculated from baseline (first dose date of IMP). Assessments that fall outside of this window will not be considered as being per protocol. However, all such assessments will be included into analysis and listings.

For the patients who early discontinued from the study, the End of Study visit will be mapped to the corresponding scheduled visit based on the study day.

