4.5 Analysis of the primary endpoint

The change from baseline in DAS28-CRP at week 12 will be analyzed using the method described in Section 2.4.1.

The primary analysis will be performed on the Per-protocol set (W12 PPS) which is the most conservative approach to show equivalent efficacy as this analysis set is the “cleanest” sample of the study population to identify differences, if there are any.

The MMRM will include the patient into the analysis as long as there is at least one non-missing DAS28-CRP change from baseline value.

The stratification factors in the primary analysis model will use the data from clinical database as it is most correct data and there are known incorrect stratification assignments in IRT data.

Table 4-1 MMRM Analysis SAS® Code

```
/* Save the LS Means and the differences into datasets */
ods output Diff = Diff LSMeans = LSMeans;
proc mixed data=DATASETNAME method=reml covtest;
  class VISIT TREATMENT USUBJID REGION RA_MED BODY_WEIGHT;
  model CHG = BSL VISIT TREATMENT VISIT*TREATMENT REGION
    RA_MED BODY_WEIGHT / solution ddfm=KR;
  repeated VISIT / type=un subject=USUBJID;
  lsmeans TREATMENT / diff CL;           /* Overall treatment effect */
  lsmeans VISIT*TREATMENT / diff CL;   /* treatment effect per visit */
run;
```

Note: names in capitals are only placeholders for the real dataset or variable names; select the model parameter estimations at visit Week 12 only from the SAS output datasets.

Sensitivity analysis of primary endpoint:

- Repeat the primary analysis based on SP1 FAS
- Repeat the primary analysis using IRT stratification data
- Repeat the primary analysis using the statistical model with treatment as fixed effect and body weight as continuous covariate (i.e., other stratifications like region and prior therapy will be excluded from the model)
- Repeat the primary analysis using the statistical model with treatment as fixed effect only

- Repeat the primary analysis by ADA status up to Week 12 (Positive/Negative)

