4.6 Analysis of secondary endpoints

4.6.1 Efficacy evaluation

4.6.1.1 Key secondary endpoint: Time-weighted averaged change from baseline in DAS28-CRP until Week 24

The averaged change from baseline in DAS28-CRP between Week 2 and Week 24 (standardized AUEC approach), will be estimated by a weighted mean across visits. The weights are derived using the standard formula from the trapezoidal rule across the visits. Mean averaged change from baseline from Week 2 to Week 24, standard errors and the two-sided 95%/90% CI for the mean difference between GP2017 and Humira® will be estimated from the ANCOVA model and the 95%/90% CI compared to the pre-specified equivalence margin of [-0.6; 0.6].

The time-weighted averaged change from baseline is defined as the change from baseline of DAS28-CRP in Weeks 2, 4, 12 and 24, weighted based on the time intervals between the actual dates of two consecutive visits in days. The scheduled visits which are outside the allowed time window can be used for the calculation (e.g., the End of Study visit for early discontinued patients). Unscheduled visits or repeat measurements will not be used in the calculation of the time-weighted averaged change from baseline.

In general, the time-weighted averaged change from baseline will be derived using following formula:

$$\text{time weighted averaged CFB} = \frac{\sum_{i=1}^k 0.5 \times (c_i + c_{i-1}) \times (d_i - d_{i-1})}{\sum_{i=1}^k (d_i - d_{i-1})}$$

Where k = number of timepoints (will be 4 if all DAS28-CRP values up to Week 24 are present)

d_i = study day based on the actual visit dates (see Section 4.1.3)

c_i = change from baseline in DAS28-CRP on d_i , where c_0 refers to baseline and is defined as zero.

If c_m value (where $m < k$) is missing, c_m shall be set equal to c_{m-1} and $d_i = d_{i-1}$ for the calculation.

The time-weighted averaged change from baseline analysis will be performed using Analysis of Covariance (ANCOVA). The model will include following terms: treatment group, body-weight category, prior systemic therapy, and region as factors and baseline DAS28-CRP value as continuous covariate. In the case that the IRT and eCRF values of the stratification factors differ the correct definition of the stratification factors used for the analyses will be based on the clinical database.

Table 4-2 ANCOVA analysis SAS® Code

```
/* Save the LS Means and the differences into datasets */
ods output Diff = Diff LSMeans = LSMeans;

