4.6.1.2 DAS28-CRP and DAS28-ESR scores

The change from baseline in DAS28-CRP and DAS28-ESR at all visits will be analyzed using the same MMRM method as for primary endpoint analysis (see Section 2.4.1).

DAS28-CRP and DAS28-ESR at baseline and weeks 2, 4, 12, 24, 36 and 48, and DAS28-CRP and DAS28-ESR change from baseline at weeks 2, 4, 12, 24, 36 and 48, will be summarized by treatment and visit using descriptive statistics. For DAS28-CRP and DAS28-ESR, the spaghetti plots by treatment and site will be provided, individual patient profile will also be provided.

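### Do SAP 2.1.2 and 4.1.4 conflict over where an early leaver's End of Study DAS28-CRP enters the MMRM?

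*SAP*

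**What the plan says.** Four parts of the SAP bear on an End of Study (EoS) visit made by a patient who stops early.

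- **SAP 2.1.2**, in a paragraph that opens with by-visit summaries: "End of Study visit within the nominal visit windows on a condition of absence of a nominal visit will be assigned" to the nominal visit, with a cross-reference to 4.1.4; "otherwise it will be included as a separate visit regardless of the day it took place".
- **SAP 4.1.4** sets windows of ±2 days (Study Period 1) and ±3 days (Study Period 2). It says of out-of-window assessments that "all such assessments will be included into analysis and listings". In a separate paragraph it says that for early discontinuers "the End of Study visit will be mapped to the corresponding scheduled visit based on the study day".
- **SAP 4.6.1.1**, for the time-weighted average (AUEC) only, allows scheduled visits "outside the allowed time window can be used for the calculation (e.g., the End of Study visit for early discontinued patients".
- **SAP 2.4.1 and 4.5** define the primary MMRM on "DAS28-CRP change from baseline up to Week 12 as the endpoint", with "repeated VISIT / type=un subject=USUBJID" in Table 4-1. Neither mentions EoS records. SAP 4.6.1.2 says that DAS28-CRP and DAS28-ESR at all visits "will be analyzed using the same MMRM method as for primary endpoint analysis".

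The primary set, W12 PPS, holds only patients who completed Week 12 (SAP 2.7.2). The SP1 FAS repeat is a sensitivity analysis.

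**The concern.** Out-of-window EoS records are to be expected. Protocol Section 6 asks for the final visit as soon as possible after discontinuation, so it can fall on any day, while DAS28 is scheduled after baseline only at Weeks 2, 4, 12, 24 and 48 (protocol 6.4.1). On its face, SAP 2.1.2 keeps such a record separate and SAP 4.1.4 moves it to a scheduled visit.

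If 4.1.4 is taken to mean the nearest visit, two things could happen. A value from several weeks before Week 12 could be entered as Week 12. Or a patient who attended Week 12 and left soon afterwards could have two Week 12 records, which an unstructured covariance indexed by visit cannot handle. Two programmers could then build different input data for a confirmatory equivalence model, and the choice between two written rules might go undocumented.

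**Working it through.** **1. The plan's own figure.** Inputs from SAP 2.5.1: true difference 0, SD 1.30, margin 0.6, 246 evaluable (123 per arm).

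SE = 1.30 × √(2/123) = 0.1658, and 0.6/0.1658 = 3.62. Power = 2Φ(3.62 − z) − 1.

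- 90% CI (z = 1.645): 95.2%
- 95% CI (z = 1.960): 90.3%

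The stated 95% and 90% reproduce, and 123/0.8 rounds up to 154 per arm. The EoS rule does not enter this calculation.

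**2. What nearest-visit mapping would do.** DAS28 targets are Days 15, 29, 85 and 169, with a window of ±2 days. Assume visits are attended on the target day. The midpoints are Days 22, 57 and 127.

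| EoS day | Result under nearest-visit mapping | Days |
|---|---|---|
| 2–12, 23–26, 58–82 | off-window value in an empty slot | 11 + 4 + 25 = 40 |
| 13–15, 27–29, 83–85 | same as SAP 2.1.2 | 9 |
| 16–21, 30–56, 86–126 | second record at an attended visit | 6 + 27 + 41 = 74 |
| 22, 57 | tie | 2 |

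The total is 125 days (Days 2–126). The 74 and the 40 exist only if 4.1.4 means nearest visit and the absence condition in 2.1.2 is set aside.

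**3. Route into the primary analysis.** Leavers before Week 12 are not in W12 PPS. That leaves EoS on Days 86–126 in patients who already have a Week 12 value. The Week 12 window ends on Day 87, so 39 of those 41 days lie beyond it, and the model covers data up to Week 12.

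With the protocol's 20% dropout spread evenly (assumption):

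- over Days 2–336: 308 × 0.20 × 41/335 = 7.5 patients
- over Days 2–168 (all dropout before Week 24): 308 × 0.20 × 41/167 = 15.1 patients

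Both are counted on all randomized patients, before PPS exclusions and refused final visits.

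**4. What a duplicate does.** For records at Weeks 2, 4, 12 and 12, rows 3 and 4 of the patient's residual covariance block are identical. The rank is 3 of 4 and the determinant is 0, so the likelihood cannot be evaluated. The run fails visibly; it does not give a quietly different estimate.

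**5. Size in W12 PPS.** Simulation of 6,000 trials, 123 per arm, true difference 0.6, leaving at Weeks 14–18, with the attended Week 12 value replaced by the later EoS value (which neither section prescribes). The shift is 0.000 with 5% leaving per arm, 0.006 at 4% v 7%, and 0.016 at 9% v 16%.

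**6. Size in SP1 FAS.** Two simulations with different assumptions, 154 per arm:

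- *4,000 trials per scenario, true difference 0.6.* SD 0.9 (Week 2) rising to 1.3 (Week 12); correlation with Week 12 of 0.57, 0.66 and 0.77 at Weeks 2, 4 and 8; withdrawal at Weeks 6, 8 and 10. The two rules differ by 0.002–0.005 with 10% unrelated withdrawal per arm, and by 0.019–0.033 with withdrawals of 11% v 18%. In the latter case the estimate is 0.570 under 2.1.2 and 0.589–0.603 under nearest-visit mapping.
- *300 trials per scenario, true difference 0.* Mean changes −1.0, −1.5 and −2.2 at Weeks 2, 4 and 12; SD 1.3; correlations 0.5–0.7; withdrawal on Days 16–82; EoS mean change −0.3 or −1.0; EoS value used only in an empty slot. With dropout 10 points apart the mean estimate moves by 0.05–0.10. With equal dropout the mean stays near 0 under both rules, and the within-trial gap averages 0.04–0.07. Success on the 95% CI changes by between about +1 and −4 points across scenarios.

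**The case for a change.** The strongest case for acting is that the input to a confirmatory model should follow from the SAP text alone. SAP 4.1.4 does omit both conditions, and 4.5 names no rule. If 2.1.2 governs only by-visit summaries, 4.1.4 is the only rule left for the model, and it is the one that could create duplicates. The stated fallback for non-convergence, another covariance structure, would not cure a duplicate, because any structure indexed by visit gives the same singular block. A clarifying sentence would cost almost nothing.

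The omission stands, and so does the point about the fallback. The rest is weaker. SAP 4.1.4 says corresponding, not nearest, and 2.1.2 sends the reader there. The visit corresponding to a study day is then the one whose window contains it, subject to the conditions just given. The statement that out-of-window assessments are analysed precedes the EoS sentence and concerns data recorded for scheduled visits. Nothing makes EoS a level of VISIT in the model. The AUEC rule is specific to an endpoint built on actual dates, so it does not contradict the other two. The repair for a duplicate is already in 2.1.2: an EoS record fills a slot only when the nominal visit is absent.

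**Conclusion.** No change to the plan is needed. This is a drafting gap that analysts would fill sensibly: one record per patient per scheduled visit, with the attended visit kept. The primary W12 PPS analysis is exposed only under a reading that adds nearest to 4.1.4 and ignores both the absence condition and the Week 12 limit. Even then the failure is visible, and the simulated effect of using the later value is at most 0.016 against 0.6.

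The live ambiguity concerns mainly the SP1 FAS sensitivity MMRM and the by-visit models of SAP 4.6.1.2. The FAS simulations give shifts from 0.002 to about 0.10, the larger ones when dropout differs between arms. Withdrawal rates, timing, correlations and EoS values are all assumed, and the first FAS simulation also needs a way of resolving duplicates that the SAP does not supply. The size is therefore indicative only.

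Enforcing 2.1.2 throughout would not clearly improve the estimate. With withdrawals of 11% v 18% and a true difference of 0.6, that rule gave 0.570, further from the truth than the 0.589–0.603 from mapping. The choice is a trade-off, and the equivalence conclusion does not depend on it.
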